## **1.b. Association between fracture type, fracture trauma type and bone mineral density**

*First author:* [name]

*Co-authors:* (in random order) [name]; [name], [name]; [name], [name]; [name].

*Last author:* [name]

*Study design:* Prospective multi-center cohort study

*Participants:* Approx. 200 individuals aged 18-60 years

*Exposure:* Acute, non-pathological hip fracture (intra- and extracapsular) regardless of trauma level

*Study groups:* High and low bone mineral density; high and low trauma injuries.

*Aim:*

1. Analysis of association between bone mineral density at the time of hip fracture (DXA scan) and fracture type.

Statistical analysis of categorical data using Chi-square test.

2. Analysis of association between trauma type and fracture type.

Statistical analysis of categorical data using Chi-square test.

*Collected variables in the prospective study:*

Fracture pattern (femoral neck fracture – undisplaced and displaced; basocervical fracture; trochanteric fracture – stable and unstable; subtrochanteric fracture)

Type of trauma (other than low-energy, low-energy)

DXA scan at the time of the fracture

For adjustment:

Gender, age, BMI

Comorbidity, medication

Diet

Abuse – alcohol, drugs, tobacco, anabolic steroids

Socioeconomics (working capacity, type of living)

Fracture history (own and first-hand relatives)

Laboratory tests including hormonal status

Physical / functional level prefracture (New mobility score and others)

Health-related quality-of-life prefracture

*Hypotheses:*

There is no association between low BMD and displaced/unstable hip fracture

There is no association between higher trauma energy and displaced/unstable hip fracture.

There is an association when both low BMD and higher trauma energy exists and displaced/unstable hip fracture.

*Perspective/clinical relevance:*

To understand the interaction between trauma energy level and bone strength (as measured by DXA) and fracture type.

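### SAP 1.b groups continuous BMD into high and low with no cut-point and names only a chi-square test, which cannot serve its adjustment list or its interaction perspective

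*SAP*

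**What the plan says.** All of this is in SAP section 1.b unless stated otherwise.

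- **Groups:** "High and low bone mineral density; high and low trauma injuries". Trauma is then defined as low-energy or other than low-energy. BMD gets no threshold, scale (g/cm², T-score or Z-score) or site, here or in the protocol.
- **Aim 1:** "Analysis of association between bone mineral density at the time of hip fracture (DXA scan) and fracture type". Aim 2 is the same for trauma type.
- **Method, under each aim:** "Statistical analysis of categorical data using Chi-square test". No other method is named.
- **Hypotheses:** "There is no association between low BMD and displaced/unstable hip fracture"; "There is no association between higher trauma energy and displaced/unstable hip fracture"; and "There is an association when both low BMD and higher trauma energy exists and displaced/unstable hip fracture".
- **Perspective:** "To understand the interaction between trauma energy level and bone strength (as measured by DXA) and fracture type".
- **Adjustment:** at least 17 items are listed for adjustment, with no model to use them.
- **Fracture pattern:** neck and trochanteric fractures carry a displaced or stable split. Basocervical and subtrochanteric fractures do not: "basocervical fracture; trochanteric fracture – stable and unstable; subtrochanteric fracture".

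The section gives about 200 participants. The protocol (Material and Method) projects 200 to 300, calls the study mainly descriptive and gives no power calculation. SAP 1.a compares BMD with control cohorts and also names only chi-square, but states no split.

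**The concern.** Three things are at stake.

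1. **Information.** Splitting a continuous predictor discards the differences within each group. If risk changes smoothly with BMD, a real moderate association is more likely to be missed. Hypothesis 1 predicts no association, so a miss could be taken as support for it.
2. **An open choice.** With no cut, scale or site fixed, the grouping can be chosen after the data are seen. For a moderate effect that choice can decide the verdict.
3. **Questions the named test cannot answer.** A simple chi-square takes no covariates, so the adjustment list has no analysis attached. A chi-square on the joint low-BMD, higher-energy group can address hypothesis 3 as worded. It does not isolate the interaction in the perspective, because separate effects of BMD and energy also make it significant.

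**Working it through.** The plan states no power or effect size, so there is no figure of its own to reproduce. From the documents: n of about 200 (SAP 1.b), with 300 as the protocol's upper figure; the binary displaced/unstable outcome (1.b hypotheses); two-level trauma. Assumed, not in the documents: normal BMD, effect linear on the logit scale, half of fractures displaced or unstable, all patients usable, two-sided 5%, no adjustment. Cuts that call 50, 25 or 20% of patients low are illustrations.

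**1. Information kept by a split, weak effect.** Efficiency = φ(z_p)²/[p(1−p)], with p the share called low.
- p = 0.50: 0.3989²/0.25 = 0.637, a loss of 36%
- p = 0.25: 0.3178²/0.1875 = 0.539, a loss of 46%
- p = 0.20: 0.2800²/0.16 = 0.490, a loss of 51%

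**2. Power at OR 1.5 per SD lower BMD, n = 200.** Power = Φ(√(nλ) − 1.96), with λ the per-patient noncentrality.
- Continuous: the covariance of BMD and outcome is 0.0975, so λ = 0.0975²/0.25 = 0.0380 and power = Φ(2.76 − 1.96) = 0.79.
- Split: λ = p(1−p)(difference in risk)²/0.25. Risks in low and high groups are 0.579 and 0.421 (p = 0.50), 0.625 and 0.458 (0.25), 0.637 and 0.466 (0.20). λ = 0.0248, 0.0208, 0.0188; power = 0.61, 0.53, 0.49.
- Simulation gives 0.79 against 0.63, 0.55, 0.51. Hence about 79% against 62/54/50%.

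**3. Other effect sizes, and dependence on the cut (simulation, n = 200).** The last column is the share of cohorts in which chi-square verdicts at cuts of 20, 25, 33 and 50% are not all the same.

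| OR per SD | Continuous | 50% low | 25% low | 20% low | Verdicts differ |
|---|---|---|---|---|---|
| 1.0 | – | – | – | – | 13% |
| 1.2 | 25% | 19% | 16% | 15% | 28% |
| 1.5 | 79% | 62% | 54% | 50% | 46% |
| 2.0 | 99% | 96% | 92% | 89% | 15% |

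At OR 1.5 and n = 300, disagreement is 38%. With 70% displaced or unstable and n = 200, power at OR 1.5 is 73% against 54/42/37%.

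**4. Joint-group chi-square with no interaction (simulation, n = 200).** Let BMD have OR 1.5 per SD and energy OR 2.0, with additive logits. With half higher-energy, the test is significant in about 74/59/53% of cohorts (52 to 75% across repeat simulations). With 30% higher-energy it is 62/46/41%.

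**5. Interaction power (simulation, n = 200, half higher-energy, no BMD effect in low-energy patients).** For OR ratios of 1.5, 2.0 and 2.5 per SD, continuous BMD gives 28, 63 and 82%; a median split gives 20, 44 and 63%.

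**6. What a null result could exclude.** With no true effect, the unadjusted 95% CI is about exp(±1.96/√(200 × 0.25)) = exp(±0.277) = 0.76 to 1.32 per SD.

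**7. Effect of adjustment.** If covariates explained 20 to 30% of BMD variance (assumed), 80% power would fall to Φ(2.80√0.8 − 1.96) = 71% or Φ(2.80√0.7 − 1.96) = 65%. The upper limit in step 6 would rise to 1.36 or 1.39. An adjusted split would lose power too.

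**8. Room for covariates.** Seventeen listed items plus BMD and energy make at least 19 terms. If 30 to 50% of 200 patients fall in the smaller outcome class (60 to 100, assumed), that is 60/19 to 100/19, about 3 to 5 per term. BMD, energy, age and sex alone leave 60/4 to 100/4, or 15 to 25.

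**The case against.** - **The study is mainly descriptive.** The protocol says so, and that limits the severity. But 1.b states three hypotheses and a significance test, and the protocol promises risk factor analysis.
- **The chi-square sentence covers categorical data only.** True: it is silent on continuous data and does not forbid regression. A reader might infer that the plan rules out adjustment, or that chi-square is invalid. The text supports neither; it supports only that no method is given for the adjustment and interaction it announces.
- **No median split is planned.** Correct. A reader might take a 36% loss as a property of this plan. It is the weak-effect figure for one possible cut, given normal BMD and linear risk. Nor do the documents suggest that several cuts will be tried; the disagreement figures show only how much the open choice can matter.
- **A clinical threshold may be intended, and risk may step there.** Possible. If risk does step at the cut, the split loses nothing. The threshold would still need to be written down.
- **Hypotheses 1 and 2 may simply be null-hypothesis wording.** They may. That a non-significant result would be read as support is a risk, not something the documents show.
- **The binary outcome modelled here is not the literal aim.** Aim 1 speaks of fracture type, with six patterns listed; displaced/unstable appears only in the hypotheses. The figures apply to the hypotheses, and the SAP should say which table is meant.

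**Conclusion.** The gap in the text is certain: a continuous measurement is grouped with no cut-point, scale or site, and the only test named serves neither the adjustment list nor the interaction perspective. The size is conditional. In the moderate range, around OR 1.5 per SD at n = 200, the split costs some 17 to 29 percentage points of power (79 − 62 to 79 − 50), and the choice of cut often changes the verdict. At OR 1.2 both approaches usually miss; at OR 2 or more both usually succeed. All of these figures, including the 79% and the interval of 0.76 to 1.32, are unadjusted and rest on the assumptions listed. The joint-group result does not make hypothesis 3 untestable; it means that a significant test there cannot by itself be reported as an interaction.

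This should be changed, because the remedy is cheap, but it does not invalidate the study. The fracture-pattern and 1.a points are secondary gaps in specification.

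**What to change.** In SAP 1.b:

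1. **Main analysis for hypotheses 1 and 2:** logistic regression of displaced/unstable fracture on continuous BMD at one DXA site named in advance (OR per cohort SD) and trauma energy. Adjust for a short pre-specified set, for example age and sex; further listed covariates go into sensitivity analyses.
2. **Exploratory second model for hypothesis 3 and the perspective:** add the BMD-by-energy interaction, and report the BMD OR in each energy group and the OR ratio with 95% CIs. It is exploratory because an OR ratio of 1.5 per SD has only about 28% power at n = 200.
3. **Functional form:** fix it in advance. Use a spline fit as a sensitivity analysis, not as a replacement triggered by a linearity test.
4. **Interpretation:** report 95% CIs, and do not read a non-significant result as evidence of no association.
5. **High/low BMD table:** keep it for description, at one cut-point fixed in advance.
6. **Outcome:** state how basocervical and subtrochanteric fractures enter displaced/unstable, or that they are left out. The protocol's Garden and AO classification does not visibly settle this.

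In SAP 1.a, compare BMD with the control cohorts as a continuous variable, and keep chi-square for categorical variables.

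The cost is SAP wording and modest extra analysis, with no new data. Results per SD are less simple to read than a high/low contrast, and a linear term is the less efficient choice if risk truly steps at a cut; the spline sensitivity analysis is there to help show that.

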patient reported outcome during two years following the hip fracture. Patients aged 18 to 59 years, who sustain an acute non-pathological hip fracture (defined by ICD-codes S72.00, S72.10 and S72.20) and are treated within four weeks at any of the participating hospitals, are invited to participate in the study. All patients are invited, regardless of medical, cognitive and functional pre-fracture status. The patients' informed consent is to be obtained before inclusion in the study.

Participating hospitals and approximate annual number of hip fractures in patients under 60 years:

- Skåne University Hospital (Malmö and Lund, Sweden) - 45
- Hvidovre Hospital (Copenhagen, Denmark) - 50
- Odense University Hospital (Odense and Svendborg, Denmark) - 50
- Kolding Hospital – part of Lillebælt Hospital (Kolding, Denmark) - 50

The projected number of included patients in the study is 200 to 300 individuals, which would require inclusion during one and a half to two years at all units, depending on the degree of patients accepting inclusion in the study. The study is mainly descriptive, wherefore power calculations are not considered feasible.

Patients are treated according to the department's standard rationale. In addition, the study will comprise interview and written enquires, blood tests regarding medical, hormonal and nutritional status, bone density measurement (DEXA scans), magnetic resonance imaging (MRI) and follow-up visits with x-ray and functional assessment. The x-ray controls are standardized to follow the standard guidelines of Hvidovre Hospital and Skåne University Hospital, which at most means three more x-rays for some patients (in total approximately 1mSv with minimal life time risk of cancer). In patients accepting study participation, the researchers are allowed to read hospital files regarding pre- and postoperative health status. Patients will be followed for two years after inclusion. Analysis of hormonal status, health profile and bone density are compared to a standard population. Risk factor analysis will be performed, regarding the risk of sustaining a hip fracture per se as well as the risk of complications and re-operations after hip fracture treatment.

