MRI with metal artefact reduction technique (MRI MARS) is performed in patients with a femoral neck fracture, dislocated and non-dislocated treated with internal fixation, to assess signs of femoral head necrosis. MRI MARS is performed early postoperatively and at follow up visits at 4 and 12 months postoperatively. In Malmö, MRI MARS is performed using Siemens commercially available standard sequences (MARS + VAT) for metal reduction imaging together with intravenous gadolinium contrast.

Patients not meeting for follow-ups will be called upon three times, thereafter they are contacted by phone, to complete the interview normally performed at the visit.

Assessment of radiographs will be performed using standardized definitions, by one of the local researchers from each of the departments and [name] will co-assess all radiographs.

Recorded data

Basic demographic indicators:

HFU-60

Gender

Age

Type of living (alone, together with someone else, institution, lacks permanent residence)

Extent of work (full time, part time, sick leave, disability pension, not working for other reason)

Health indicators:

BMI

Comorbidity (ASA and Charlson)

History of previous fractures – patient recall and medical files

Hospital admission during the year preceding the hip fracture

Use of particular medication during 5 years leading up to the fracture

Use of tobacco, alcohol or other recreational drugs – prefracture –AUDIT- and DUDIT-questionnaire.

Physical activity level

Bone mass density – DEXA scan

Regular menstruation

Laboratory blood tests:

Test:

- hemoglobin, leucocytes w. differential count, platelet count, erythrocyte sedimentation rate and/or C-reactive protein (a.s.a.p. after trauma)
- electrolytes (Na⁺, K⁺), creatinine
- total calcium + albumin, parathyroid hormone (a.s.a.p. after trauma)
- 25-hydroxyvitamin D
- alkaline phosphatase, INR
- TSH, T3, T4
- testosterone (men) / estradiol (women)
- tissue transglutaminase antibody

Purpose:

- normal blood samples and pathological
- renal function
- hypo-/hyperparathyroidism
- vitamin D deficiency
- bone metabolism, liver disease
- thyroid disease
- hypogonadism
- coeliac disease

Regarding the injury:

Information about the accident – mechanism of injury, other injuries apart from hip fracture.

Fracture type classification according to Garden (displaced vs. undisplaced) and AO – classified by local researcher, not surgeon.

Type of surgery and implant.

Outcome:

Patient reported outcome measure (PROM):

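### SAP 1.b tests fracture type with a pooled chi-square and leaves hospital off its adjustment list; if hospitals differ in both trauma mix and recorded fracture type, pooling can create or hide an association

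*SAP*

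**What the plan says.** SAP 1.b describes a multi-centre cohort of about 200 patients. Both of its aims carry the same single line of method: "Statistical analysis of categorical data using Chi-square test". No stratified test and no regression model is named.

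For the second aim ("Analysis of association between trauma type and fracture type") the exposure has two levels ("Type of trauma (other than low-energy, low-energy"), and the hypothesis is a stated null: "There is no association between higher trauma energy and displaced/unstable hip fracture".

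A list of adjustment variables follows. It opens with "Gender, age, BMI" and continues through comorbidity, medication, diet, substance use, socioeconomic factors, fracture history, laboratory tests, prefracture function and quality of life. Hospital, centre and country are not on it.

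The protocol (Material and Method) lists four hospital groups with approximate annual numbers. The first is "Skåne University Hospital (Malmö and Lund, Sweden) - 45"; the other three, all Danish, are given 50 each.

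Under Recorded data, fracture type is "classified by local researcher, not surgeon". Under the Follow-up scheme, radiographs are assessed "by one of the local researchers from each of the departments". The same sentence says that standardised definitions are used and that one person co-assesses every radiograph. It does not say how a disagreement is settled or which reading enters the analysis.

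**The concern.** Hospital can be related to both sides of the table. Trauma mix may differ between hospitals, and so may the share recorded as displaced or unstable, through real case mix or through the local reader's threshold. If the hospitals with more higher-energy injuries also record more displaced or unstable fractures, the pooled table shows an association even when there is none inside any hospital. If the pattern runs the other way, pooling can hide a real association or reverse its sign.

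This matters for 1.b because its hypotheses concern the presence or absence of these associations, so an error in either direction bears on the conclusion. The same reasoning applies to the first aim, with bone mineral density in place of trauma type. The adjustment list shows that the authors meant to allow for other factors, but a plain chi-square test cannot use any of them.

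**Working it through.** **Inputs from the documents.** Annual numbers are 45, 50, 50 and 50, which sum to 195. The shares are 45/195 = 23% and 50/195 = 26% for each of the others, so no group dominates. For 200 patients this gives about 200 × 45/195 = 46 and 200 × 50/195 = 51 per group. The plan gives no significance level, no effect size and no rates by hospital, so it has no figure on this point to reproduce.

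**Assumptions.** Two-sided 5% level; trauma type and fracture type independent inside every hospital; hospital rates as stated below. None of these rates comes from the documents.

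**One case by hand.** Take four hospitals of 50. Two have 50% higher-energy injuries and 70% displaced/unstable; two have 20% and 45%. The expected counts are:

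| | Higher energy, unstable | Higher energy, not | Low energy, unstable | Low energy, not |
|---|---|---|---|---|
| Two hospitals at 50%/70% (n = 100) | 35 | 15 | 35 | 15 |
| Two hospitals at 20%/45% (n = 100) | 9 | 11 | 36 | 44 |
| Pooled (n = 200) | 44 | 26 | 71 | 59 |

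Odds ratio in the first pair: (35 × 15)/(15 × 35) = 1.00. In the second pair: (9 × 44)/(11 × 36) = 396/396 = 1.00. Pooled: (44 × 59)/(26 × 71) = 2596/1846 = 1.41. The association comes from pooling alone.

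**False-positive rates by simulation.** There were 20,000 studies per scenario, n about 200, hospital sizes in proportion to the annual numbers, and shares evenly spaced across the four hospitals where a range is given.

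| Assumed hospital rates (higher-energy share; displaced/unstable share) | Pooled odds ratio | Pooled chi-square rejects |
|---|---|---|
| Only trauma mix differs (25-55%; 60% in all) | 1.00 | 4.9% |
| Only fracture mix differs (40% in all; 45-75%) | 1.00 | 4.9% |
| Both differ (25-55%; 45-75%), uncorrelated | 1.00 | 5.1% |
| Aligned 5-point steps (32.5-47.5%; 52.5-67.5%) | 1.05 | 5.4% |
| Aligned, 20-45%; 45-65% | 1.13 | 7.0% |
| Aligned, 20-50%; 45-70% | 1.20 | 9.1% |
| Aligned 10-point steps (25-55%; 45-75%) | 1.24 | 10.9% |
| Opposed 10-point steps (25-55%; 75-45%) | 0.81 | 11.2% |
| Two hospitals at 50%/70%, two at 20%/45% | 1.41 | 20% |

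A Cochran-Mantel-Haenszel test stratified by hospital rejected in about 5% of studies in every scenario (4.8-5.2%).

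**Effect of sample size.** At 300 patients, the top of the protocol's projected range, the aligned 10-point case rises from 10.9% to 14.0%. More patients do not remove the error.

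**The case against.** The strongest reply is that the harm needs two conditions that the documents do not show. Hospitals must differ on both trauma mix and recorded fracture type, and the differences must line up. With the shares 20-50% and 45-70% assigned to hospitals in all 24 possible orders, the false-positive rate averages 6.4% and the mean odds ratio is about 1.00. In the two-against-two case, if the high-unstable hospitals are one from each trauma pair, the rate returns to about 5%. This stands: the 20% figure is a possibility under a sharp and fully aligned split, not an expectation.

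The second reply is that common definitions and one co-assessor of all radiographs act directly on differing local thresholds. This also stands in part. They weaken the reader route, though without a rule for disagreements they do not close it. They leave the case-mix route untouched.

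Third, the protocol calls the study mainly descriptive, and a stratified test might seem more than it needs. But 1.b states hypotheses and names a test for them, so the choice of test still matters.

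A reader might go further and infer that local classification by itself produces a false trauma effect. It does not: when only recorded fracture type differs between hospitals, the test keeps its level. A reader might also extend the point to the laboratory comparisons in SAP 1.a. The documents do not say which laboratories are used, so that extension has no support.

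**Conclusion.** The concern holds as a gap in the analysis method of SAP 1.b, for both aims. The chi-square is pooled, it adjusts for nothing, and hospital is missing from the adjustment list of a study with four hospital groups.

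The size cannot be known from the documents. Under the assumed rates, false positives range from about 5% (small, uncorrelated or one-sided differences) through 7-11% (aligned ranges of 20 to 30 points) to 20% (the two-against-two split), and the bias can go in either direction. The documents do not support the stronger inference that the planned result will be spurious, or that hospitals in fact differ in this way. The case for a change rests on the possibility of a misleading result and on the low cost of preventing it.

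**What to change.** For both aims of SAP 1.b, make the main analysis a logistic regression of displaced/unstable fracture on the exposure (trauma type or bone mineral density). Include hospital group as a fixed effect (3 degrees of freedom) and a short prespecified subset of the listed covariates, such as age and gender. The model has to be named: adding hospital to the list alone changes nothing while the only stated method is a chi-square test.

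At minimum, replace the pooled chi-square with a Cochran-Mantel-Haenszel test stratified by hospital group. This handles hospital but none of the other listed covariates.

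In either case, show the hospital-specific odds ratios descriptively; with about 50 patients per group they will be imprecise. State which reading defines fracture class, for example the co-assessed one, and use it throughout. The binary outcome also needs a rule for the basocervical and subtrochanteric categories, which SAP 1.b lists without a stable/unstable split.

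The cost is SAP wording and a small loss of precision from three extra parameters. Treating hospital is not named in the protocol's lists of recorded data, but it is assumed to be known for every patient, so no new data collection should be needed.

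### SAP 1.b does not say how its six fracture patterns become the displaced/unstable outcome of its hypotheses, or how fracture location is handled in the chi-square tests

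*SAP*

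**What the plan says.** SAP 1.b has two aims. The first is "Analysis of association between bone mineral density at the time of hip fracture (DXA scan) and fracture type"; the second is "Analysis of association between trauma type and fracture type". Each is followed by the same analysis line: "Statistical analysis of categorical data using Chi-square test". No table layout or degrees of freedom are given.

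The only fracture coding in 1.b stands under the collected variables: femoral neck, split into undisplaced and displaced, then "basocervical fracture; trochanteric fracture – stable and unstable; subtrochanteric fracture". That is six levels, combining site with displacement (neck) or stability (trochanteric).

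The hypotheses use a different outcome. The first reads "There is no association between low BMD and displaced/unstable hip fracture", the second "There is no association between higher trauma energy and displaced/unstable hip fracture", and the third "There is an association when both low BMD and higher trauma energy exists and displaced/unstable hip fracture".

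1.b also lists covariates for adjustment; fracture location is not among them. The protocol (Recorded data, Regarding the injury) records the Garden dichotomy and the AO class, with no rule for combining them. The protocol (Material and Method) calls the study mainly descriptive and gives no power calculation.

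**The concern.** The aims and the hypotheses name different outcomes, and nothing in the text leads from one to the other. Basocervical and subtrochanteric fractures have no displaced or unstable status in 1.b, so part of the cohort has no defined outcome under the hypotheses.

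Two of the hypotheses are stated as no association. A rejection caused by a shift between neck and trochanteric fractures could be reported as overturning them. A non-rejection from a test that spreads the effect over several degrees of freedom could be reported as supporting them. While the table is unspecified, the choice between six levels and two can also be made after the data are seen.

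**Working it through.** The documents state no power, category shares or effect size, so there is no figure to reproduce. The inputs from the documents are six patterns, two BMD groups and two trauma groups (SAP 1.b), and N of about 200 (SAP) or 200 to 300 (protocol). Everything else is assumed: two-sided alpha 0.05, the group split, the location shares and the displaced/unstable shares.

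**Formula.** For groups with shares f and 1−f, and category probabilities p1 and p2 with weighted mean p̄, the noncentrality is λ = N·f(1−f)·Σ(p1−p2)²/p̄. The rejection probability is that of a noncentral chi-square with 5 df (six levels) or 1 df (binary). With N = 200 and a 50:50 split, N·f(1−f) = 50.

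**Six levels, location difference only.** Assume neck 65% vs 50%, trochanteric 20% vs 35%, basocervical 5% and subtrochanteric 10% in both groups, and a displaced/unstable share of 60% everywhere.
- Neck undisplaced: 0.26 vs 0.20, giving 0.06²/0.23 = 0.0157
- Neck displaced: 0.39 vs 0.30, giving 0.09²/0.345 = 0.0235
- Trochanteric stable: 0.08 vs 0.14, giving 0.06²/0.11 = 0.0327
- Trochanteric unstable: 0.12 vs 0.21, giving 0.09²/0.165 = 0.0491
- Sum 0.1210, so λ = 50 × 0.1210 = 6.05. With 5 df the test rejects about 44% of the time (43% by simulation).

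The displaced/unstable share is (0.39 + 0.12)/0.85 = 60% in one group and (0.30 + 0.21)/0.85 = 60% in the other, so the binary test rejects about 5%. Across assumed neck-share differences of 15 to 20 points and splits of 50:50 or 30:70, the six-level test rejects 34–75% at N = 200.

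**Crude 2×2, location difference only.** Let the share differ by site: 75% displaced in neck, 40% unstable in trochanteric, the same in both groups. Assume neck 70% vs 50% and trochanteric 15% vs 35%.
- Group 1: (0.70×0.75 + 0.15×0.40)/0.85 = 0.585/0.85 = 68.8%
- Group 2: (0.50×0.75 + 0.35×0.40)/0.85 = 0.515/0.85 = 60.6%

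There is no difference within either site, yet the pooled shares differ by 8.2 points. The crude test rejects 21% with the two unlabelled patterns left out, and 18% with subtrochanteric coded unstable and basocervical not.

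**Three analyses side by side.** N = 200, 50:50, about 60% neck and 28% trochanteric, 70% displaced within neck and 40% unstable within trochanteric (all assumed). Ranges are across separate simulation runs.

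| Scenario | Six levels | Crude 2×2 | Stratified by location |
|---|---|---|---|
| 10-point location shift only | 18–20% | 7–8% | 5% |
| 20-point location shift only | 71–72% | 15–17% | 5% |
| True odds ratio 2 at both sites | about 33% | about 54% | about 57% |

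**Power, same effect at both sites.** Assume the share is 50% vs 70% in both neck and trochanteric fractures, with location 55/5/30/10% (neck, basocervical, trochanteric, subtrochanteric).
- Six levels: λ = 50 × (0.11²/0.22 + 0.11²/0.33 + 0.06²/0.12 + 0.06²/0.18) = 50 × 0.1417 = 7.08. With 5 df, power is 51%.
- Binary without the two unlabelled patterns (N = 170): λ = 42.5 × (0.20²/0.60 + 0.20²/0.40) = 7.08. With 1 df, power is 76%.
- Binary with subtrochanteric coded unstable and basocervical not: 69.5% vs 52.5%, λ = 50 × (0.17²/0.61 + 0.17²/0.39) = 6.07. Power is 69%.

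The first two carry the same λ; only the degrees of freedom differ. At N = 300 the powers are 71%, 91% and 86%.

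**Where the power loss disappears.** With an effect in neck fractures only (80% vs 50%, N = 200), six-level power is 73% and binary power 67–74%. With opposite effects (neck 75% vs 50%, trochanteric 35% vs 65%), it is 80% against 11%.

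**The case against.** A reader might infer that the SAP plans a 2×6 test. It does not say so. The six patterns stand under collected variables, the analysis line names only a chi-square test, and the hypotheses fit a collapsed 2×2. This stands, so the six-level consequences are conditional. It does not remove the gap: the collapsed table also needs a rule for two patterns, and it still mixes location with displacement.

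A reader might also call every location-driven rejection a false positive. Against the aims as worded it is not: location is part of fracture type, so a six-level rejection is a valid answer to them. For the crude 2×2, the hypotheses carry no within-site condition, so a location shift creates a true marginal association. What fails is reading either result as evidence that BMD or trauma energy is linked to displacement or instability at a given site.

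That the six-level test always has less power is not supported either. The loss needs effects in the same direction across sites, and most of it is recovered by collapsing alone (33% to 54%, against 57% stratified).

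Nor do the documents show that basocervical and subtrochanteric fractures must be excluded. AO is recorded, the hypotheses exclude no hip fracture, and a stated mapping would serve.

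Finally, the adjustment list shows that more than a raw chi-square is foreseen. Location is not on that list, so it does not close the gap.

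**Conclusion.** The concern holds in conditional form. The outcome for the 1.b hypotheses is undefined, and the only coding listed mixes location with displacement/stability. Tested at six levels, a significant result may reflect location alone and does not answer the hypotheses. Tested as a crude 2×2, it can still be moved by location when the displaced/unstable share differs by site.

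The sizes given illustrate what can happen at N = 200 under assumed shares, splits and effects; they are not predictions for this cohort. That the outcome and the handling of location are unspecified follows from the text and needs no assumption. This should be settled before analysis. It does not call the data collection into question.

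**What to change.** For the 1.b hypotheses, define a binary outcome: displaced versus undisplaced in femoral neck fractures, unstable versus stable in trochanteric fractures. Analyse it stratified by or adjusted for fracture location, by Mantel-Haenszel or by logistic regression with a location term. Report the two site-specific estimates as well, because a pooled test can miss opposite effects.

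State in advance how basocervical and subtrochanteric fractures are handled, either by a stated mapping or by describing them separately, with a sensitivity analysis for the other choice. Report the association of BMD and trauma type with fracture location as a separate question, which keeps the aims as worded.

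The cost is SAP wording, since location, displacement and stability are already collected. The small downside is that the two unlabelled groups may contribute little or nothing to the main contrast.
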